**SECTION I: RESEARCH PLAN**

1. **Statement of Purpose:** State the scientific aim(s) of the study, or the hypotheses to be tested.

Aim 1: Does lactation improve insulin sensitivity and increase lipolysis in women?

In this Aim, we will assess whether lactation amongst women with a history of GDM will improve whole body insulin sensitivity as well as increase whole body lipid turnover by using hyperinsulinemic-euglycemic clamps combined with [6,6-2H]-glucose and [2H5]-glycerol infusions. These stable, non-radiating isotopes have been used extensively and safely to study the mechanisms of insulin resistance amongst non-pregnant as well as pregnant humans; however, these techniques have not previously been applied to the study of insulin sensitivity during lactation. Our goals will be two-fold: 1) to determine whether lactation induces similar changes in insulin sensitivity in humans as in mice and 2) to pilot the feasibility of performing larger, more detailed metabolic studies in this population of women post-partum.

Aim 2: Retrospective chart review of women with a history of GDM who had an OGTT 6-8 weeks post-partum as part of standard of care at Yale Medicine's Maternal-Fetal Medicine Clinic.

2. **Probable Duration of Project:** State the expected duration of the project, including all follow-up and data analysis activities.

5 years

3. **Background:** Describe the background information that led to the plan for this project. Provide references to support the expectation of obtaining useful scientific data.

Our premise is that lactation protects against the development of Type 2 Diabetes Mellitus (T2D) by mobilizing tissue triglycerides (TGs) and fully reversing the insulin resistance (IR) of pregnancy. A growing body of epidemiological data has indicated that nursing protects against T2D in all women but particularly amongst women with gestational diabetes mellitus (GDM) (1-8). However, no studies have investigated the detailed molecular mechanisms underlying these beneficial effects of lactation. Many studies have

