Screening visit (Visit 1): For women who did not attend the post-partum OGTT visit or who are not patients at the MFM Clinic, they will be consented at this visit. All participants will be screened at the YNHH Research Unit (HRU) or Church Street Research Unit (CSRU) with a medical history and exam. Blood will be collected for HbA1C, Cr, ALT, AST, TSH, hematocrit and fasting lipid panel, and a urine pregnancy test will be administered. Oral glucose tolerance tests (OGTT) will be performed after an overnight fast. A nurse will insert an intravenous (IV) catheter and subjects will ingest 7.5 oz of glucola, which contains 75 g of glucose in flavored water. Blood samples will be taken at certain time points before and after glucola ingestion for the measurement of plasma glucose and insulin concentrations. Approximately 60 mL of blood will be drawn at this visit.

Continuous glucose monitor (CGM) placement (Visit 2): For up to 10 days prior to Visit 3, eligible participants will be asked to wear a CGM (Dexcom G6 Pro). At the visit for CGM placement (either at CSRU or HRU): 1) a trained study staff member will explain to the participant how to use the CGM, and 2) a trained study staff member will insert the CGM's plastic wire-like tip under the participant's skin with the use of the CGM applicator. This visit will take approximately 15 minutes.

The CGM consists of a sensor that measures glucose levels from the interstitial tissue. A transmitter that captures and stores data from sensor. The sensor is sterile and comes in an unopened package. Each sensor and transmitter are single use only and disposable. The Dexcom G6 Pro does not require any calibration. This means that no finger sticks are required for its use. Participants will need to return the sensor within 30 days of sensor placement.

The Dexcom G6 Pro data is blinded to study participants. Study staff will explain to the participants that intense exercise may cause the sensor to loosen due to sweat or movement of the sensor. If the CGM sensor/transmitter falls off while the participant is wearing it, we will ask them to return to the HRU or CSRU so that a new sensor/transmitter can be re-inserted. Subjects will be provided with our contact information in the event that they have any questions, concerns or issues related to the CGM.

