After completing the 10-day CGM session, the sensor will be removed by a trained study staff member. To remove the sensor, the adhesive patch will be gently peeled off from the skin. Removal of the sensor is a painless procedure. The sensor/transmitter will be discarded after use. CGM removal will occur during Visit 3.

Hyperinsulinemic-euglycemic clamp (Visit 3): After an overnight fast, eligible subjects will return to the YNHH HRU. Two IV catheters will be inserted: one into a distal arm or hand vein that will be placed in a heated box to allow for the sampling of arterialized venous blood; the second into an antecubital vein for administration of a primed (200 mg/m^2) and continuous infusion of [6,6-2H] Glucose and [2H5] Glycerol

(non-radioactive stable isotopes) as well as for collecting blood samples for insulin and glucose measurements. After an equilibration period lasting 2 hours., the 2-step euglycemic-hyperinsulinemic clamp study will be performed. A primed-continuous infusion of regular insulin will be given at 8 mU/(m^2 × min) during the first 2 hours, and increased to 40 mU/(m^2 × min) for the subsequent 2 hours. Plasma glucose levels will be measured every 5 min, and a variable glucose infusion will be initiated to maintain levels at ~90 mg/dl. Plasma samples will be drawn at baseline and throughout the infusion period for measurement of isotope enrichment, insulin, NEFA, glycerol turnover, and additional hormones which may be altered with lactation. Approximately 160 mL of blood will be drawn at this visit.

Also at this visit, we will perform indirect calorimetry a total of 3 times (once before and twice during the insulin clamp). A transparent plastic hood will be placed over the participant's head for 30 minutes each time. A hose connects the hood to a calorimeter, which measures oxygen consumption and carbon dioxide production and calculates resting energy expenditure.

After the insulin clamp is completed, body composition will be assessed using whole body DXA. The DXA scan will be performed in the HRU to measure fat distribution, body fat, lean body mass and bone density.

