- Group 1: 16 women (ages 18-45, HbA1C < 6.5%) with a history of GDM who exclusively or mostly breast-fed (< 6 ounces of formula/24 hours at 6-9 weeks of delivery) for at least 4-6 months and who delivered within the past 18 months
- Group 2: 16 women (ages 18-45, HbA1C < 6.5%) with a history of GDM who exclusively or mostly formula-fed (no breastfeeding or < 3 weeks of breastfeeding) and who delivered within the past 18 months

7. **Subject classification:** Check off all classifications of subjects that will be specifically recruited for enrollment in the research project. Will subjects who may require additional safeguards or other considerations be enrolled in the study? If so, identify the population of subjects requiring special safeguards and provide a justification for their involvement.

 Children	 Healthy	 Fetal material, placenta, or dead fetus
 Non-English Speaking	 Prisoners	 Economically disadvantaged persons
 Decisionally Impaired	 Employees	 Pregnant women and/or fetuses
 Yale Students	 Females of childbearing potential	

NOTE: Is this research proposal designed to enroll children who are wards of the state as potential subjects?

Yes  No

8. **Inclusion/Exclusion Criteria:** What are the criteria used to determine subject inclusion or exclusion?

Aim 1:

Inclusion Criteria:

- Women between the ages of 18-45 with a history of GDM (as defined as the American Diabetes Association criteria) who delivered a singleton, live birth at  $\geq$  35 weeks gestation within the past 18 months
- HbA1C < 6.5% at time of screening
- Delivery within the past 18 months
- Group 1: exclusively or mostly breast-fed (< 6 ounces of formula/24 hours at 6-9 weeks of delivery) for at least 4-6 months

Exclusion criteria:

- Currently lactating or lactation within the past 1 month at the time of the screening visit
- Diagnosis of diabetes (T1D or T2D) prior to pregnancy
- Current use of any glucose-lowering agents
- Pregnancy related medical problems including preeclampsia
- Major congenital fetal anomalies
- Creatinine > 1.5mg/dL, Hematocrit < 35%, ALT and AST > 2.5X upper limit of normal

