- Screening and Informed Consent Discussion: Research team members will contact interested potential participants to assess eligibility and provide the participant with additional information about the study, including the study procedures, purpose and potential complications. The brief screen via email or phone will ask for the following information to confirm study eligibility:

- Name
- Age/Date of Birth
- Place of Birth
- Phone Number/Email
- Address
- Marital Status
- Race/Ethnicity

- Height/Weight
- Medical/Surgical History including obstetric history
- Medications
- Drug/Alcohol Use

It is necessary to collect this information prior to the subject traveling to Yale for an in-person screening visit, in order to determine their eligibility and avoid unnecessary screening and traveling on the part of the participant. This information will be protected according to HIPAA policies and will be destroyed if the individual is determined to not be eligible for the study during this correspondence or is otherwise not interested in participating in the study, unless the subject consents for his/her screening information to be stored for future studies that he/she may be eligible for.

During the in-person screening session, the informed consent form and study details are reviewed in detail by one of the project investigators or key study personnel and the subject will be asked to read the informed consent form (approved by the Yale Human Investigation Committee). The subject will be given time to ask questions and only after that will the subject be asked to give informed consent to participate. The informed consent form and study details will again be reviewed with the subject on each study day prior to beginning the study.

The Principal Investigator in this study or key study personnel will be responsible for obtaining consent.

c. Who is recruiting potential subjects?

All research team members as well as the individuals listed above (JDAT, referring providers, etc.).

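### The only pregnancy test described is at screening; none is described before the Visit 3 insulin clamp and DXA, so it should be repeated at Visit 3

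*Combined protocol and SAP*

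**What the plan says.** Section I, item 4 (Research Plan) sets out three research visits.

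- **Visit 1 (screening).** Alongside the screening bloods and the OGTT, "a urine pregnancy test will be administered". No other pregnancy test is described.
- **Visit 2 (CGM placement).** "For up to 10 days prior to Visit 3, eligible participants will be asked to wear a CGM". On removal, the plan says "After completing the 10-day CGM session, the sensor will be removed by a trained study staff member" and "CGM removal will occur during Visit 3".
- **Visit 3 (clamp).** Women found eligible have stable-isotope infusions, a two-step insulin infusion of 2 hours per step, about 160 mL of blood drawn and indirect calorimetry. Then, "After the insulin clamp is completed, body composition will be assessed using whole body DXA". No pregnancy test appears among these procedures.

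Item 8 (Inclusion/Exclusion Criteria) admits women aged 18-45 and does not list current pregnancy as an exclusion. The HbA1C criterion is assessed at screening, and so is the lactation exclusion: "Currently lactating or lactation within the past 1 month at the time of the screening visit".

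Items 10 and 11 (Risks, Minimizing Risks) and Section II, part B (Drugs/Biologics) add no repeat test. No contraception requirement and no longest permitted interval between Visits 1 and 3 is given. The only step repeated on every study day is in Section III, items 3 and 6: "The informed consent form and study details will again be reviewed with the subject on each study day prior to beginning the study".

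**The concern.** Every participant could become pregnant, and the one test precedes the most demanding visit by an interval that the protocol does not cap. A woman who conceives after Visit 1, or whose pregnancy was too early to show then, could go through the clamp and the DXA with no test in the protocol to detect it. Item 12 (Data and Safety Monitoring Plan) rates the clamp and glycerol infusion as more than minimal risk, and item 10 names hypoglycaemia as a clamp risk. The risk sections do not discuss an undetected pregnancy, so nothing shows that leaving out a second test was a considered decision.

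What is at stake is participant safety. No effect on the endpoints or the analysis is claimed.

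**Working it through.** The plan gives no figure on this point to reproduce. The check has two parts: whether the text closes the gap anywhere, and how much a second test would add.

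**1. Reading the text**

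- *Order of visits.* The CGM goes to women already found eligible, so Visit 2 cannot precede the Visit 1 assessment. The sensor comes off at Visit 3. If the session runs its full 10 days, the interval T between Visits 1 and 3 is at least 10 days. The plan says up to 10 days, so shorter wear, and hence a shorter T, is possible.
- *Eligibility wording at Visit 3.* Visit 3 is for eligible women, but this does not call for a new pregnancy check. Item 8 has no current-pregnancy criterion, and its HbA1C and lactation criteria are tied to screening.
- *Study-day review.* This goes over consent and study details. It could prompt a woman to report a pregnancy she knows of, but not one she is unaware of.

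No visible text closes the gap.

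**2. What a repeat test would add**

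Inputs:

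- T, the days from Visit 1 to Visit 3. T = 10 or more follows from a full CGM session. T = 3, 30 and 60 are illustrative.
- d, the days from conception until a urine test turns positive. This is not in the documents; d = 10 to 21 is assumed.
- A constant daily chance of conception, also assumed.

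The Visit 1 test finds conceptions at least d days before Visit 1, which is T + d days before Visit 3. With that test alone, conceptions in the last T + d days go undetected. With a second test at Visit 3, only those in the last d days do. So:

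share of the window closed = [(T + d) − d] / (T + d) = T / (T + d)

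| T (days) | d = 10 | d = 14 | d = 21 |
|---|---|---|---|
| 3 | 3/13 = 23.1% | 3/17 = 17.6% | 3/24 = 12.5% |
| 10 | 10/20 = 50.0% | 10/24 = 41.7% | 10/31 = 32.3% |
| 30 | 30/40 = 75.0% | 30/44 = 68.2% | 30/51 = 58.8% |
| 60 | 60/70 = 85.7% | 60/74 = 81.1% | 60/81 = 74.1% |

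These are shares of a time window, not probabilities that a pregnant woman is exposed. The expected number of such women would need a conception rate and a distribution of visit intervals, and the documents give neither.

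**3. Extra tests:** target enrolment is 32 (Section III, item 1), so 32 × 1 = 32.

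**The case against.** The strongest reply is that the risk is small on the protocol's own account. The isotope tracers are described in Section I, item 1 as "used extensively and safely to study the mechanisms of insulin resistance amongst non-pregnant as well as pregnant humans". The DXA dose is put at one tenth of a chest X-ray, and plasma glucose is checked every 5 minutes with dextrose at hand. Nothing in the documents identifies fetal harm from these procedures. All of this stands, and it keeps the point below a mandatory change.

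A second reply is that the Visit 1 test is not misplaced. It sits with the other laboratory checks that control entry to the later visits, and testing again on the day of the procedure is a stricter practice rather than the correction of a contradiction. That is a fair description, but a pregnancy test at entry says nothing about conceptions in the weeks that follow.

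Third, a physician or nurse practitioner determines eligibility (item 9) and supervises the clamp (items 10 and 11). This puts a clinician in charge but requires no test.

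Fourth, the size estimate depends heavily on T. Only the 10-day row is tied to the documents, and the formula gives no credit for pregnancies a woman already knows about. Those are likeliest at long intervals, so the 30- and 60-day rows are the most likely to overstate the gain. This also stands, and those rows should be read as illustration.

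Finally, the consent form was not available for this review, and an instruction there, or a standing procedure of the research unit, may already call for a same-day test. The finding is limited to what the protocol describes.

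**Conclusion.** The concern holds. A woman can follow the plan as written and reach the clamp and DXA with no test since screening, at least 10 days earlier if she completes the CGM session. At that interval a second test closes 32-50% of the untested window. If CGM wear is cut short and T is 3 days, it closes 13-23%. These figures rest on the assumed 10- to 21-day detection delay and the constant chance of conception. The second test narrows the gap without closing it, because conceptions in the last 10 to 21 days would still be missed.

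The absence of a current-pregnancy exclusion is a drafting matter, since a screening test implies that a positive result excludes. Overall this is a modest safety improvement that should be made, held with medium confidence.

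**What to change.** 1. Repeat the urine pregnancy test on arrival at Visit 3, before any infusion and before the DXA, and do not proceed if it is positive.
2. At the study-day review already planned, ask about possible recent conception, because a urine test can miss it.
3. Add current pregnancy or a positive pregnancy test to the exclusions in Section I, item 8, so that both tests have a stated consequence.

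The cost is about 32 test strips at a visit already held, one question, one eligibility line and an occasional cancelled Visit 3. Sample size, power, alpha and the number of visits do not change. If same-day testing is already unit practice, the change is only to write it down.

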Oral glucose tolerance test (OGTT): The OGTT is a commonly used outpatient test for diagnosis of type 2 diabetes and gestational diabetes. It is not associated with any specific adverse effects. Occasionally, some patients may experience mild nausea or GI discomfort following drinking the 75-gram glucose drink; however, this typically resolves after eating food.

Hyperinsulinemic-euglycemic clamp: The infusion of insulin and glucose poses a small risk that plasma glucose will fall below the predetermined level (90-100 mg/dL) resulting in little or no symptoms of hypoglycemia: sleepiness, hunger, anxiety, diaphoresis and tremor exaggerated symptoms. These symptoms are quickly reversed with IV dextrose infusion. The risks of drawing blood and inserting an IV line are detailed above. The studies will be performed under the supervision of a qualified physician or nurse practitioner. All solutions that are administered via IV will be sterile, pyrogen free, and prepared in a sterile environment. During glucose infusion, D20 (20% glucose) will be used to decrease the risk of thrombophlebitis that is associated

with hypertonic glucose solutions. To avoid hypoglycemia during the hyperinsulinemic clamp, plasma glucose will be checked every five minutes using a bedside glucose monitor. Based on these measurements, the plasma glucose will be adjusted via the D20 infusion.

Phlebotomy: The total amount of blood drawn for this study is 220 mL (including screening, OGTT and hyperinsulinemic-euglycemic clamp). People who are in good health are not usually affected by this kind of blood loss. However, to be safe, subjects will be warned against donating blood for at least 6 weeks before and after completing this study. Additionally, subjects are screened for anemia at the first visit and women with a hematocrit less than 35% will be excluded.

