IV Insertion and Blood Drawing: Risks of bruising, clotting, and infection will be minimized by having venipuncture performed by trained, experienced personnel under sterile conditions. To avoid injury due to fainting, the antecubital vein catheter will be inserted when the subjects are recumbent. All infused solutions will be prepared in sterile form by the YNHH Investigational Drug Services (IDS) pharmacy and tested for pyrogenicity and sterility before use. During studies 20% dextrose will be used to reduce the risk of thrombophlebitis associated with use of excessively hypertonic glucose solutions (50% dextrose). Women with a hematocrit less than 35% will be excluded. Patients will be advised to refrain from blood donation for 6 weeks after study completion.

Hyperinsulinemic-euglycemic clamp: The infusion of insulin and glucose poses a small risk that plasma glucose will fall below the predetermined level (90-100 mg/dl) resulting in hypoglycemia, which can be quickly reversed with IV dextrose infusion. To avoid hypoglycemia during the clamp, plasma glucose will be checked every five minutes using a bedside glucose monitor. Based on these measurements, the plasma glucose will be adjusted via the dextrose infusion. The risks of drawing blood and inserting an IV line are detailed above. The studies will be performed under the supervision of a qualified physician or nurse practitioner. All solutions that are administered via IV will be sterile, pyrogen free, and prepared in a sterile environment. During glucose infusion, dextrose 20 (20% glucose) will be used to decrease the risk of thrombophlebitis that is associated with hypertonic glucose solutions (50% glucose).

6,6D2-glucose and D5-glycerol: The infusion of 6,6D2-glucose and D5-glycerol involves no radioactivity, and the glucose and glycerol are metabolized just as the unlabeled metabolites. Clinical research studies using these tracers have been used at Yale for decades with no adverse effects. The isotopes are purchased from (Cambridge Isotopes, Inc.) in powder form which has been certified to be sterile and free of pyrogens. They are made into a solution by the YNHH IDS. The solutions are tested to be free of pyrogens and to be sterile before being administered to the participants. All certifications are kept with the IDS.

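### The clamp description attaches insulin and glucose sampling to the catheter that infuses the tracers, not to the heated catheter placed for arterialized sampling

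*Combined protocol and SAP*

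**What the plan says.** Section I, item 4 (Research Plan), Visit 3 sets out the two catheters in one sentence, divided by a semicolon.

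- The first goes into a distal arm or hand vein kept in a heated box, "to allow for the sampling of arterialized venous blood".
- The second is described as "the second into an antecubital vein for administration of a primed" and continuous infusion of the labelled glucose and glycerol. The sentence then closes with "non-radioactive stable isotopes) as well as for collecting blood samples for insulin and glucose measurements".

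The order of events follows: "After an equilibration period lasting 2 hours", the two-step clamp is run, with 2 hours at each insulin rate. Two later sentences describe sampling. One says "Plasma glucose levels will be measured every 5 min, and a variable glucose infusion will be initiated to maintain levels at" a target level. The other has plasma drawn at baseline and "throughout the infusion period for measurement of isotope enrichment, insulin, NEFA, glycerol turnover", among other measurements. Neither names a catheter.

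**The concern.** A catheter in a heated vein is placed so that the sampled blood is arterialized. The same sentence then gives the sampling of insulin and glucose, two core clamp measurements, to the other catheter, which is carrying tracer.

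If staff did what the sentence says, two things would follow. The samples would be ordinary antecubital venous blood, so the heated box would serve no purpose for them. They would also be drawn through a line with an infusion running that contains labelled glucose. Either could distort the measured values. Section I, item 1 (Aim 1) measures whole body insulin sensitivity with the clamp, and item 13 makes it a primary endpoint. The sentence is part of the operative procedure, not background.

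**Working it through.** No arithmetic applies, because the protocol gives no figure to reproduce on this point. The check is of the wording, set side by side.

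**1. What the clause attaches to.** After the semicolon the only catheter in play is the antecubital one. It is given two parallel purposes: administering the tracers, and collecting samples for insulin and glucose. The parenthesis that opens the quoted words describes the tracers just named, so the sentence runs on without a gap and the second purpose belongs to the same catheter as the first. Attaching it to the heated catheter is possible as a guess at intent, but not as a reading of the sentence.

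**2. Whether timing explains it.** Samples taken from the antecubital catheter before any infusion began would be harmless. The text does not fit that. The 2-hour equilibration comes before the clamp, and the five-minute glucose measurements belong to the clamp. Insulin is among the samples drawn "throughout the infusion period for measurement of isotope enrichment, insulin, NEFA, glycerol turnover". The tracer infusion is described as continuous. No stop time is given, so that it runs through the clamp is an assumption, though sampling for isotope enrichment during the clamp implies it.

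**3. What the rest of Visit 3 suggests.** The later sampling sentence lists insulin with isotope enrichment in the same plasma samples. That points to a single sampling line, presumably the heated one, and so to a misplaced clause. It is an inference, and no sentence says so.

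**4. Whether another section settles it.**

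| Place | What it says | Names a sampling site? |
|---|---|---|
| Section I, item 10 (Risks), clamp | Glucose is checked every five minutes; "Based on these measurements, the plasma glucose will be adjusted via the D20 infusion" | No |
| Section I, item 11 (Minimizing Risks), IV insertion | "the antecubital vein catheter will be inserted when the subjects are recumbent" | No; it concerns posture at insertion only |
| Section I, item 11, clamp | Repeats the five-minute check | No |
| Section II, B, opening text | Names the tracers and gives the insulin infusion rates | No |
| Section II, B, item 2 (Background Information) | Repeats the five-minute check | No |

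None of these reassigns the clause, and none says which catheter supplies the five-minute readings.

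**5. Whether a size can be put on it.** It would take at least the tracer concentration at the sampling point, the difference between arterialized and antecubital venous values, and the line that carries the insulin and the 20% dextrose. The protocol gives a tracer priming dose (200 mg/m²) but no continuous rate or concentration. It gives no arterialized-to-venous difference, and no line for insulin or dextrose. Neither size nor direction can be derived.

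**The case against.** The strongest reply is that this is a slip of drafting that no trained clamp team would follow. The heated catheter's purpose is plain. The two roles are not strictly exclusive, since the protocol never says that only the heated line may be sampled. Item 4 answers a form prompt that asks for lay language, so it was not written as a bench procedure. The study is at one site, and the clamps are run under clinical supervision.

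Much of that stands. A misplaced clause is the likeliest explanation, and the conflict is between assigned roles rather than a logical impossibility. It does not dispose of the point. The document cites no separate clamp procedure that would override the sentence, and the intended reading has to be inferred from a different sentence.

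The reply is also right that the five-minute readings should be kept apart from the quoted clause. Items 10 and 11 and Section II describe those readings as bedside checks, and nothing assigns them to either catheter. A reader might infer that the values steering the dextrose infusion come from the infusing line. The documents do not say that. They leave the site unstated, which is a gap to close rather than an error to allege.

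**Conclusion.** The point holds and is minor. The sentence is wrong as written, not merely short of detail: it attaches insulin and glucose sampling to the infusing antecubital catheter although a separate catheter is placed for arterialized sampling, and no other section corrects it. If followed, it could distort the measurements behind whole body insulin sensitivity, by an amount and in a direction that cannot be computed. The conclusion rests on the ordinary grammar of the sentence and on the assumption that the tracer is running when clamp samples are drawn.

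Some stronger readings are tempting but not supported:

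- **Insulin as a secondary endpoint.** Item 13 lists insulin levels without tying them to the clamp, and the Visit 1 glucose tolerance test also measures insulin. Harm to that endpoint is not established.
- **Extra variability between staff.** Nothing in the document suggests that some staff would follow the wording and others the intent.
- **Scale from the number of readings.** Counting scheduled five-minute readings would measure no error, and would presume a sampling site that the text does not give.
- **Bias between feeding groups, or error in isotope enrichment and lipid turnover.** The same procedure applies to both groups, and the quoted clause names only insulin and glucose.

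**What to change.** In Section I, item 4, Visit 3, reconcile the two halves of the catheter sentence so that the insulin and glucose sampling clause sits with the catheter the protocol already designates for arterialized sampling. Have the study team add a statement of which catheter supplies the five-minute clamp glucose readings. Item 4, items 10 and 11, and Section II, B all leave this open, and it is for the team to settle.

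The cost is one clause moved and one short statement added. No procedure, sample or participant is added, and the analysis in item 13 is unaffected.
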